6.6.2.3 Hospitalizations for Recurrent CDI

The number of subjects requiring hospitalization due to recurrent CDI through 8 weeks following the completion of the study treatment will be summarized, along with the length of hospital stay, the number of subjects requiring ICU admission, and the length of ICU stay during hospitalization.

A listing of all hospitalizations due to CDI throughout the study will be generated.

6.6.2.4 Rate of onset of new chronic conditions for those treated with RBX2660

Documentation of physician diagnosed chronic conditions for all subjects will be completed at Baseline and compared to new physician diagnosed chronic conditions reported at 1-week, 4-weeks, 8-weeks, 4 months and 6 months. Chronic condition is defined as a condition lasting >3 months. This will be presented as a rate of chronic conditions onset for the combined first and second enemas, as well as separately for first and second enemas.

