6.6. Safety Endpoints

1. Number of adverse events per subject

2. Timing of attributable TEAEs
3. Duration of TEAEs
4. Relatedness of TEAEs
5. Severity of TEAEs
6. Causality of TEAEs to IP, enema, *C. difficile* or prior condition
7. Number of each of the following CDI-related TEAEs through 8-weeks post treatment: death, septic shock, toxic megacolon, colonic perforation, emergency colectomy, and ICU admission
8. Onset of new chronic conditions relative to treatment administration

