10.5. Screening Visit

The following study activities/data will be collected/conducted at the Screening visit:

- Subjects are told about the study and informed consent is obtained (enrollment)
- Assign the subject number.
 - The format for subject number will include site code, followed by study-specific identifier, and 3-digit subject number assigned in sequential ascending order. For example: AAAOLS, RBX08-###. Where “AAA” is your study site’s code, and “###” is the subject’s number following a -001, -002, -003,... format.
- Standard demographics: gender, ethnicity, date of birth, race
- Relevant medical history, including comorbidity index variables (see **Section 16**)
- CDI medical history documentation will be collected
- Assess inclusion/exclusion criteria
- Measure vital signs: height, weight, blood pressure, pulse, breathing rate and temperature
- Physical exam (no genitourinary exam unless medically indicated) is performed to establish a study baseline health status (findings that can be attributed to the subject’s medical history):
 - General
 - HEENT (head, eyes, ears, nose and throat)
 - Cardiovascular
 - Gastrointestinal

- Musculoskeletal
- Neurological
- Blood samples are collected and analyzed at the central laboratory for:
 - CD4 count
 - CBC w/differential
 - Comprehensive metabolic panel (CMP): Sodium, potassium, chloride, BUN, creatinine, albumin, AST, ALT, alkaline phosphatase, bilirubin (direct, indirect and total), glucose
 - C-reactive protein (CRP)
- NOTE: the results of the absolute neutrophil count (ANC) and CD4 tests must be confirmed ≥ 1000 cells/ μ L and $\geq 200/\text{mm}^3$, respectively*
- Onsite urine pregnancy test for subjects of child bearing potential
- Complete the Cdiff32 health-related quality of life questionnaire completed by the subject (see **Section 17**)
- Document concomitant medications taken within the last 30 days
- Completion of the Subject Diary is explained and how to complete it is demonstrated; see **Section 10.3**
- Record employment status
- For subjects who consented to the Optional Stool Sample collection, remind them to obtain and ship a stool sample to Rebiotix anytime between their Screening visit and their Baseline visit dates

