Hepatitis A (IgG)	
Hepatitis B Anti-Hepatitis B surface antigen	
Hepatitis C Antibody	
Treponema Antibody	

The following information is collected specific to the administration of the IP:

- Enema clinical batch number
- Enema administration start and end time
- Enema administration status (successful; attempted, not completed; opened, not administered)
- Subject position for enema
 - Length of time subject was in position after enema
- Did the Rebiotix kit components perform as expected
- Note whether the subject expelled or leaked any of the IP during the observation period

- How long was the enema retained before the expulsion or leakage (minutes)
- What was the estimated amount of enema that was expelled or leaked

Following successful completion of the above listed items, IP is administered via enema per the Instructions for Use and standard site procedure; see **Section 9.8.3**. Subjects remain at the site under supervision for at least one hour post-IP administration for vital sign assessment (temperature, heart rate, blood pressure, respiratory rate) about every 15 minutes and observation. If the subject's vital signs do not return to the pre-administration values $\pm 20\%$, assess the subject for a possible AE.

All safety data collected are to be recorded and reported as required in **Section 11**.

The subject is sent home after completion of study procedures including a review of the Subject Diary instructions, and is requested to call the study site if symptoms recur or at the onset of an adverse event.

10.9. 1-week In-Office Visit

The 1-week follow-up visit is to occur within the window of ± 3 days from the Baseline visit. All safety data collected are to be recorded and reported as required in **Section 11**.

The following study activities/data is collected at the 1-week follow-up visit:

- Review of the subject diary for solicited events as defined in **Section 11.4**
- Assess recurrence of CDI
- Subject's weight
- Adverse event collection, including new onsets of obesity, metabolic syndrome, pre-diabetes, diabetes and/or autoimmune disorders
- Cdiff32 health-related quality of life questionnaire completed by the subject
- Changes to concomitant medications since the last visit
- For subjects who consented to the Optional Stool Sample collection, remind the subject to collect and ship a stool sample to Rebiotix

10.10. 4-week Telephone Assessment

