10.13. Unscheduled Possible Recurrence Visit

If CDI recurrence is suspected any time within 8 weeks of the last study enema due to new onset documentation of three or more unformed/loose (i.e., Bristol Stool Scale type 6-7) stools within 24 or fewer consecutive hours for at least two consecutive days, possible treatment failure should be assessed. An in-office visit should occur if a recurrence of CDI is suspected. The subject must provide a fresh stool sample for shipment to the central laboratory to test for the presence of *C. difficile*.

The following study activities/data will be collected at the Unscheduled Possible Recurrence visit:

- Collect fresh stool sample to send to the central laboratory for analysis
- Assess recurrence of CDI
 - Start date of symptoms, current symptoms, central laboratory testing result, source of episode (*CDI recurrence, healthcare contagion, community contagion, or unknown*), treatment(s)
- Vital signs: temperature, pulse, blood pressure, respiration
- Adverse event collection, including the new onsets of obesity, metabolic syndrome, pre-diabetes, diabetes and/or autoimmune disorders
- Changes to concomitant medications since last visit
- Cdiff32 health-related quality of life questionnaire
- For subjects who consented to the Optional Stool Sample collection, remind the subject to collect and ship a stool sample to Rebiotix.

Treatment failure (CDI recurrence) is defined as:

- The presence of CDI diarrhea within 8 weeks of administration of a study enema, which includes a positive stool test for *C. difficile* as determined by the central laboratory.

To ensure consistency across clinical sites for the determination of study failure, the central laboratory will perform the required C. DIFF QUIK CHEK COMPLETE® Test (QCC Test) rapid enzyme immunoassay test for glutamate dehydrogenase (GDH) and toxins A and B.

In the case of suspected treatment failure where there is an immediate concern for subject safety, including the potential for serious adverse events, a test may be conducted at the site or other laboratory known to the site **in addition to** sending a sample to the central laboratory for testing. In the event the test results from the central laboratory differ from that of a local laboratory, the results from the central laboratory will be used in determination of treatment failure and eligibility to receive a second treatment with RBX2660, instead of the other laboratory's result.

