11.5. Preexisting Condition

A preexisting condition, including abnormal physical exam findings, is one that is present at the start of the study and is to be recorded at the time of the Screening visit. A preexisting condition is only to be recorded as an adverse event if the frequency, intensity or the character of the condition worsens during study participation.

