Connective Tissue Disease: Yes No

Diabetes Mellitus: Yes No

Type: Type I Type II

End-organ damage: Yes No

Chronic Kidney Disease (Moderate to severe): Yes No

Liver Disease: Yes No

Severity: Mild Moderate Severe

Hypertension: Yes No

Hemiplegia: Yes No

Chronic Pain: Yes No

Dementia: Yes No

Migraines: Yes No

Depression: Yes No

Anxiety: Yes No

Anemia: Yes No

Leukemia: Yes No

Malignant Lymphoma: Yes No

Solid Tumor: Yes No

Metastatic: Yes No

Eczema: Yes No

Acne: Yes No

Psoriasis: Yes No

AIDS/HIV: Yes No

Parkinson's Disease: Yes No

Rheumatoid Arthritis: Yes No

Systemic Lupus Erythematosus: Yes No

Sjogren's Syndrome: Yes No

CREST Syndrome: Yes No

Scleroderma: Yes No

Chronic Urinary Tract Infections: Yes No

Irritable Bowel Syndrome: Yes No

Crohn's Disease: Yes No

Ulcerative Colitis: Yes No

Peptic Ulcer Disease: Yes No

History of Constipation: Yes No

Gastroparesis: Yes No

Gastroesophageal Reflux Disease (GERD): Yes No

Alopecia (hair loss): Yes No

17. Cdiff 32 Health-Related Quality of Life Questionnaire

To be completed by the subject

DAILY ACTIVITIES

Over the last 7 days, because of your *C. diff* infection,

1. Have you had any difficulties and/or disruption carrying out your daily activities?

 1	 2	 3	 4	 5
Not at all	A little bit	Moderately	Quite a bit	Extremely

2. Have you had any difficulties carrying out your leisure activities like gardening, walking, etc?

 1	 2	 3	 4	 5
Not at all	A little bit	Moderately	Quite a bit	Extremely

3. Has it taken you longer to perform certain tasks at work (including work in the home)?

 1	 2	 3	 4	 5
Not at all	A little bit	Moderately	Quite a bit	Extremely

4. Has your *C. diff* infection prevented you from leaving your house?

 1	 2	 3	 4	 5
Never	Rarely	Sometimes	Often	Always

ANXIETY

5. Are you afraid that your *C. diff* infection could come back again?

 1	 2	 3	 4	 5

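### Follow-up asks by name about obesity, metabolic syndrome and pre-diabetes while Screening does not, and SAP 6.6.2.4 does not define a new condition, so the single-arm rate of new chronic conditions may be biased upward

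*SAP*

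**What the plan says.** Protocol 6.6 gives as its eighth safety endpoint "Onset of new chronic conditions relative to treatment administration", and SAP 5.4.2 repeats it. SAP 6.6.2.4 sets out the analysis: "Documentation of physician diagnosed chronic conditions for all subjects will be completed at Baseline and compared to new physician diagnosed chronic conditions reported at" weeks 1, 4 and 8 and months 4 and 6. It adds that "Chronic condition is defined as a condition lasting >3 months" and presents a rate for the first enema, the second enema and both combined.

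**Follow-up side.** Protocol 10.9 (1-week visit) collects "Adverse event collection, including new onsets of obesity, metabolic syndrome, pre-diabetes, diabetes and/or autoimmune disorders". The same line stands in 10.10, 10.11, 10.12 and 10.14.1, and almost word for word in 10.13 for the unscheduled recurrence visit.

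**Baseline side.** Protocol 10.5 collects "Relevant medical history, including comorbidity index variables", the latter being the yes/no list in Section 16. That list has the line "Diabetes Mellitus: Yes No" with type and end-organ damage, and it names several autoimmune diseases. It has no line for obesity, metabolic syndrome or pre-diabetes, and no open item for other autoimmune disorders. Screening also takes height, weight, a physical exam and a metabolic panel that includes glucose. Protocol 11.5 says that a preexisting condition "is one that is present at the start of the study and is to be recorded at the time of the Screening visit".

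**The concern.** The endpoint is a before-and-after comparison, so it works only if both sides are ascertained equally well. Here three conditions are prompted by name after treatment and are left to unprompted history before it. Any error this causes runs mainly in one direction: an old condition that surfaces under the later prompt adds to the count of new ones.

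In a controlled trial such an error would tend to affect both arms and largely cancel in the comparison. In this single-arm study it goes straight into the reported rate. The conditions concerned are ones that the protocol itself chose to watch for after a microbiota product. If true onset within about six months is uncommon, a few misclassified cases could distort the rate.

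**Working it through.** The plan gives no figure for this endpoint, so there is none to reproduce. The check sets the passages side by side and then illustrates the size.

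**Step 1. Are the two lists the same?**

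| Condition | Named at follow-up (10.9–10.13, 10.14.1) | Named at Screening (Section 16) |
|---|---|---|
| Obesity | Yes | No |
| Metabolic syndrome | Yes | No |
| Pre-diabetes | Yes | No |
| Diabetes | Yes | Yes |
| Autoimmune disorders | Yes, as a class | Several diseases, no general item |

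The one later contact without the named list is the second-enema visit itself (10.14), which asks about adverse events in general.

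**Step 2. What stops an old condition from being counted as new?**

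| Safeguard | What it stops | What still passes |
|---|---|---|
| Open medical history (10.5) and the recording rule (11.5) | Conditions known and reported at Screening | Conditions undiagnosed, or left out of the history |
| Adverse event rule (11.1) | Conditions known to be present at Screening, unless they change in severity or seriousness | Conditions nobody recognised as already present |
| Request for new onsets (10.9 onward) | Old conditions recognised as old | Old conditions first noticed when prompted |
| Treatment-emergence rule (SAP 5.4.3.4) | Events with a full onset date before the first enema | Year-only onset in the year of the enema, which counts as treatment-emergent; and SAP 6.6.2.4 does not invoke this rule |
| Duration of more than 3 months (SAP 6.6.2.4) | Short-lived conditions | Long-standing ones, because duration says nothing about when onset occurred |

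**Step 3. Does the SAP use the Screening measurements?** Height and weight would give BMI, but SAP 6.3 only summarises them and specifies no BMI or obesity flag. Glucose is in the Screening panel, yet the Baseline laboratory item in SAP 6.3 names hematology only. SAP 6.6.2.4 uses none of these. Reporting starts at week 1, when weight is measured again (10.9). Obesity first recorded then is far more likely to be old than new, and no rule excludes it.

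**Step 4. Size, as an illustration.** False new cases of one condition = N × p × m, where:
- N = 750, the treatment cap (Protocol 12.1);
- p = proportion with the condition before the enema, **assumed** 0.10 to 0.40;
- m = share of those missed at Screening and reported later, **assumed** 0.02 to 0.20, with 0 for a complete history.

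| p | m = 0 | m = 0.02 | m = 0.05 | m = 0.10 | m = 0.20 |
|---|---|---|---|---|---|
| 0.10 | 0 | 1.5 | 3.75 | 7.5 | 15 |
| 0.20 | 0 | 3 | 7.5 | 15 | 30 |
| 0.40 | 0 | 6 | 15 | 30 | 60 |

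For example, 750 × 0.20 × 0.02 = 3 and 750 × 0.40 × 0.20 = 60. As a rate, the non-zero cells run from 0.10 × 0.02 = 0.2% to 0.40 × 0.20 = 8.0%.

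**The case against.** The strongest reply is that the checklist is not the Baseline side of the comparison. SAP 6.6.2.4 calls for documentation of physician-diagnosed conditions and never mentions Section 16. Protocol 10.5 makes the checklist one part of a wider history, 11.5 requires every preexisting condition to be recorded, 11.1 keeps such conditions out of the adverse event data unless they worsen, and the prompt asks for new onsets. For known obesity to be counted as new, a site would have to depart from several of these rules. The case report forms are not among the documents, so the Screening form may prompt for more than the protocol shows. The endpoint is also secondary to the primary safety endpoint, is described without tests, and drives no decision rule.

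Most of this stands, and it makes the bias conditional. It does not remove it. Each rule depends on someone knowing at Screening that the condition was present, and none supplies the prompt.

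A reader might go further and infer three things that the documents do not support:
- That a condition missing from the checklist has no Baseline record and so becomes new automatically. Open history, physical exam and 11.5 contradict this.
- That questioning starts only after treatment. History is taken at Screening; what differs is prompting by name.
- That diabetes is protected and obesity is not. Obesity is the easiest of the three unlisted conditions to verify, because height and weight are measured.

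**Conclusion.** The concern holds in a limited form. The prompts are unequal, and SAP 6.6.2.4 does not say what makes a condition new. A condition that was undiagnosed or omitted from the Screening history can be counted as an onset after RBX2660, and the rate may be biased upward with no comparator to reveal it.

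The size cannot be derived from the documents. It is zero if the Screening history is complete. The illustrated 1.5 to 60 subjects per condition rests entirely on the assumed prevalence and miss rate, and should not be read as an estimate. The point affects one listed safety endpoint, not the primary one. It is worth correcting because the error runs mainly one way and most of what is needed is already collected.

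**What to change.** 1. **Screening checklist (Protocol Section 16).** Add obesity, metabolic syndrome, pre-diabetes and an item for other autoimmune disorder (specify), so that Screening and follow-up ask about the same conditions.
2. **Definition in SAP 6.6.2.4.** Count a condition as new only if its onset is after the first enema and it is absent from the Screening history. For obesity, also require that Screening BMI, from the collected height and weight, was below an obesity cut-off named in the SAP. State how partial onset dates are handled.
3. **Pre-diabetes and diabetes.** List reported cases with a raised Screening glucose or a relevant Baseline medication as possibly preexisting. Show the rate with and without them rather than removing them, since removal could discard genuine new cases.

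**Cost.** A few checklist items, with the protocol and form changes they entail, and one derivation rule on data already collected. The checklist helps only subjects not yet screened. For those already enrolled the rule corrects only part of the bias: one glucose value of unspecified fasting status is an imperfect check, and metabolic syndrome and autoimmune disorders cannot be checked from Screening data (the panel lists no lipids or HbA1c). It should not be presented as correcting most of the bias.

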6.6.2.5 Subject Diary including Solicited Adverse Events and Completion Compliance

All solicited adverse events recorded in the Subject Diary will be summarized utilizing frequencies (number of events), proportions (number of subjects with the event) and 95% CIs for categorical variables and using the descriptive statistics as listed in **Section 8.1** for continuous variables.

For each solicited event, severity scores will be summarized as both categorical and continuous values. For continuous summaries, severity scores will be identified as either pre-treatment or post-treatment (all diary entries captured after the first enema), and the average for each period will be calculated across individual subjects. Baseline for continuous summaries will be considered the average during the pre-treatment period. For categorical summaries, if a subject reports more than one severity score on the same date, the maximum severity will be used. Baseline for categorical summaries will be considered the last non-missing assessment prior to the enema.

For each categorical summary of event frequency, a two-sided 95% CI will be calculated using the normal approximation of the binomial.

The following summaries will be produced for the first enema:

- Frequency of severity scores on day of enema administration
- Frequency of severity scores on day 1 through 1-week post-treatment
- Frequency of maximum post-treatment severity score

Compliance in returning completed Subject Diaries will be calculated by dividing the number of diaries turned in, whether complete or not, by the number of diaries expected to be turned in. Furthermore, compliance will be summarized by calculating the proportion of subjects who turned in “complete” diaries, where complete is defined as answering all 14 daily questions (e.g.

11 solicited AE, Bristol Stool Type, New illnesses/injuries, New medications) for at least 80% of the expected number of diaries.

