3 STUDY DESIGN

3.1 General Study Design

This is an open-label, Phase 3 study to evaluate the safety and tolerability of RBX2660 in subjects with recurrent CDI.

Up to 750 subjects may be treated in this study. Consented subjects who meet all eligibility criteria are intended to be treated. Consented subjects who do not meet the eligibility criteria will be considered screen failures and will not count towards the total number of subjects treated.

Potential subjects are expected to already be taking or have just been prescribed antibiotics to control recurrent CDI symptoms at the time of enrollment (Screening visit) per the investigator's standard of care. Patients who have already completed their prescribed course of antibiotics to treat recurrent CDI are not eligible for enrollment (Screening visit) unless they have another recurrence that is treated with antibiotics.

Once the Screening visit is complete, in order to proceed to the Baseline Enema Administration:

1. Subject must meet all the inclusion and none of the exclusion criteria
2. Antibiotics will have been administered prior to the washout period
3. CDI symptoms must be under control leading into the antibiotic washout period

Control of CDI symptoms is defined as no longer meeting the symptomatic criteria for CDI diarrhea which is the passage of three or more unformed/loose (i.e., Bristol Stool Scale type 6-7) stools in 24 or fewer consecutive hours while taking antibiotics for the two consecutive days prior to the washout period. Thus, at a minimum the Subject Diary (which is started at the Screening visit) must show that symptoms are under control the two days prior to the washout period in order for the subject to receive the enema administration.

Study treatment (enema administration) is to be completed as soon as possible, but no later than 21 days after the Screening visit. A minimum of 24hr to a maximum of 72hr antibiotic washout period is required prior to administration of the study treatment.

In-office study follow-up visits occur at weeks 1 and 8 after completing the Baseline visit. Telephone assessments occur at week 4 and at months 4 and 6 after the Baseline visit. Subjects are required to keep a detailed diary to assess for solicited events from the date of Screening visit to the 1-week follow-up visit. The diary will be collected and reviewed at the Baseline visit prior to enema administration. The subject will continue to complete the diary for one week following

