The site investigator will make the initial determination of treatment success or failure based on the protocol-defined study definitions. The site investigator's assessment will then be provided to the Endpoint Adjudication Committee for independent adjudication of treatment success or failure that will be utilized for study analysis and reporting purposes. This may be done in an ongoing basis or a single meeting. Details of the EAC logistics, activity and responsibilities will be included in an EAC charter.

3.2 **Blinding**

This study is not blinded.

3.3 **Determination of Sample Size**

The purpose of this study is to assess the safety and tolerability of RBX2660 in a recurrent CDI population that is broader and more inclusive than that included in prior studies using RBX2660. In order to continue to collect prospective safety information and allow open-label treatment access to a broader population of patients, up to 750 subjects will be treated with RBX2660. As an open-label study, there are no statistical powering considerations for the revised sample size.

Subjects who have signed informed consent forms but do not meet all eligibility criteria will be considered screen failures. Subjects who withdraw for any reason prior to administration of the enema will be replaced without counting toward the sample size treatment cap of 750 subjects.

3.4 **Treatment**

Active treatment consists of one dose of RBX2660 delivered via enema.

4 **CHANGES IN THE CONDUCT OF THE STUDY OR PLANNED ANALYSES**

4.1 **Changes in the Conduct of the Study**

There have been no changes to the conduct of the study or planned analysis, however, ad hoc analyses may be performed as needed to support regulatory review.

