- Serious TEAEs by relatedness to *C. difficile* disease
- Serious TEAEs by relatedness to enema procedure
- Serious TEAEs by relatedness to preexisting condition
- Serious TEAEs resulting in subject withdrawal
- Serious TEAEs resulting in death

For the summary of AEs by maximum severity, if a subject has multiple events occurring in the same SOC or same PT, then the event with the highest severity will be counted. For AEs reported by causality, if a subject has multiple events occurring in the same SOC or same PT, the event with the highest association will be summarized.

A summary of TEAE and serious TEAE characteristics (severity, relatedness to IP, relatedness to *C. difficile* disease, relatedness to enema procedure, and relatedness to preexisting condition by outcome) will also be presented by first and second enema and overall.

Incidence of AEs and serious AEs will also be presented by onset interval separately for the first and second enemas (as applicable), as well as a combined presentation for the following intervals:

- Baseline (onset date prior to date of first enema)
- IP administration (onset date on the date of the first and second enema, as applicable)
- Intervals relative to the enema date (first and second enemas, as applicable):
 - 1-Week (day 8), 4-Weeks (day 29), 8-Weeks (day 57), 4 Months (Day 120), and 6 Months (Day 180).

For data presentation, SOC will be ordered alphabetically, with PT sorted by decreasing total frequency. No inferential statistics will be provided for the AE data.

Subject listings will be presented for all AEs including SAEs.

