7 STATISTICAL METHODS

7.1 General Methodology

Data will be summarized using descriptive statistics with SAS® Version 9.3 or higher. Confidence intervals (CI) will be constructed at the level of 95% unless specified otherwise. For continuous variables, descriptive statistics (number of subjects [N], mean, standard deviation [SD], median, inter-quartile range [IQR], minimum, and maximum) will be generated. For discrete/categorical variables, the number and percentage of non-missing subjects will be generated. Standard operating procedures (SOPs) will be followed in the creation, validation and quality control of all data displays and analyses.

Subject listings of all data from the eCRFs as well as any derived variables will be presented.

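### Normal-approximation 95% intervals for solicited diary events have no sparse-count fallback: they collapse to 0–0% at zero events and go below zero at one to three

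*SAP*

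**What the plan says.** SAP 6.6.2.5 summarises the solicited events from the Subject Diary by number of events and by "proportions (number of subjects with the event) and 95% CIs for categorical variables". It then fixes the method: "For each categorical summary of event frequency, a two-sided 95% CI will be calculated using the normal approximation of the binomial". The tables listed after that cover the first enema only ("The following summaries will be produced for the first enema"). They show severity scores on the day of the enema, severity scores from day 1 through one week, and the maximum post-treatment score. SAP 5.4.4.1 lists 11 solicited events.

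Nothing else in the documents supplies another method. SAP 7.1 sets only the level: "Confidence intervals (CI) will be constructed at the level of 95% unless specified otherwise". SAP 7.3 on missing data and Protocol 12.2 and 12.3 do not address interval methods. For adverse events in general, SAP 6.6.2.1 states "No inferential statistics will be provided for the AE data", which leaves the diary intervals as they are.

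On the denominator, SAP 3.1 states: "Up to 750 subjects may be treated in this study". SAP 3.3 says there is no powering calculation.

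**The concern.** The normal-approximation (Wald) interval takes its width from the observed proportion. When that proportion is zero the width is zero. When it is close to zero the interval is symmetric around a value near the boundary, so the lower limit becomes negative and the upper limit too low. The SAP applies this interval to every categorical summary of the diary events, whatever the count.

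The wording can mean one interval per event, or one per event-by-severity cell. Under the first reading the problem affects whichever events turn out to be rare; rectal bleeding and fever are possible candidates. Under the second, splitting 11 events by severity score and period makes small cells likely. The defect is the same wherever few subjects are affected.

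Safety and tolerability is the primary objective, and these tables are where the SAP attaches intervals to safety frequencies. A 95% interval printed as 0–0% states certainty that the data do not support, and it errs towards understating risk.

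**Working it through.** The plan gives no interval, event rate or precision figure for solicited events, so there is no figure of its own to reproduce.

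**Inputs.** Two-sided 95%, z = 1.960 (SAP 6.6.2.5 and 7.1). n = 750, the treatment cap (SAP 3.1). Event counts, true rates and smaller values of n are assumptions.

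**Planned interval.** With p̂ = x/n, the limits are p̂ ± z·√[p̂(1 − p̂)/n].

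- x = 0: p̂ = 0, so both limits are 0.
- x = 1, n = 750: p̂ = 0.133% and z·√[0.001333 × 0.998667/750] = 0.261%. The limits are −0.13% and 0.39%.
- The lower limit is negative when 0 < x < z²n/(n + z²). At n = 750 this is 3.8415 × 750/753.8415 = 3.82, so it holds for x = 1, 2 and 3. The threshold is 3.77 at n = 200 and 3.57 at n = 50, so the same counts are affected.

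**Comparison with the exact (Clopper-Pearson) interval, n = 750.** For x = 0 the exact upper limit is 1 − 0.025^(1/750) = 0.49%.

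| Events | Wald 95% | Exact 95% | Wald upper ÷ exact upper |
|---|---|---|---|
| 0 | 0 to 0% | 0 to 0.49% | 0 |
| 1 | −0.13 to 0.39% | 0.003 to 0.74% | 53% |
| 2 | −0.10 to 0.64% | 0.03 to 0.96% | 66% |
| 3 | −0.05 to 0.85% | 0.08 to 1.16% | 73% |

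**True coverage at n = 750**, by summing binomial probabilities over all x:

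| True rate | Wald | Wald upper limit below truth | Wald lower limit above truth | Exact | Wilson |
|---|---|---|---|---|---|
| 0.1% | 52.8% | 47.2% | 0.01% | 99.3% | 96.0% |
| 0.2% | 77.6% | 22.3% | 0.1% | 98.2% | 93.5% |
| 0.5% | 88.4% | 11.1% | 0.5% | 96.2% | 96.3% |

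At 0.1% and 0.2% the upper-limit misses are the probability of observing no event: 0.999^750 = 47.2% and 0.998^750 = 22.3%. At 0.5% they are the probability of zero or one event.

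**Where the method works.** At n = 750, Wald coverage is 93.7%, 92.2%, 92.2%, 94.6% and 94.9% at true rates of 1%, 1.5%, 2%, 5% and 30%. Over a grid from 1% to 2% the mean is 93.0%, with a narrow dip to 88.9% at 1.055%. With 225 of 750 affected, Wald gives 26.7–33.3% and exact 26.7–33.4%.

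**Smaller denominators (assumed).** At n = 500, zero events gives 0–0% against exact 0–0.74%, and one event gives −0.19 to 0.59% against 0.005 to 1.11%. For zero events the exact upper limit is 1.83% at n = 200 and 7.11% at n = 50, while Wald stays at 0–0%.

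**Partial remedies.** Adding a continuity correction of 1/(2n) at n = 750 gives −0.07% to 0.07% for zero events and still a negative lower limit (−0.05%) for four. Truncating at zero hides the negative limits but leaves the zero-width interval and the coverage unchanged.

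**The case against.** The strongest reply concerns weight. The documents give no rate for any single solicited event, and at event level the defect needs no more than three subjects in up to 750. In the first Phase 2 study (Protocol 5.3.1), 17 of 33 subjects (51.5%) were still reporting some solicited event on Day 7 after one treatment. If one interval per event is meant, sparse cases may be few or absent. If severity cells are meant, some may be empty by design: the severity table in Protocol 11.7 has no Grade 3 or 4 for flatulence and no Grade 4 for chills, although the SAP does not say the diary uses that scale. The low coverage at 0.1% and 0.2% is the zero-count case in another form. In absolute terms the upper limit is too low by 0.49 percentage points at zero events and 0.31 at three (1.16 − 0.85). The count is printed beside the interval, and no decision rests on it.

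All of this stands as a limit on importance. It does not rescue the rule. The 51.5% is for any event and says nothing about the rarest of the 11. In the earlier Phase 3 study (Protocol 5.3.4), only 5 of 368 TEAEs in the maximum-severity summary were potentially life-threatening. Those grades are the investigators' rather than diary scores, but they make near-empty top-severity cells plausible. The SAP text directs an invalid interval whenever such a count occurs.

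**Conclusion.** The concern holds. This is a stated rule that yields a wrong interval for sparse counts. The arithmetic is certain: 0–0% at no events, and a negative lower limit at one to three events for every denominator examined from 50 to 750. How many table entries will be that sparse is not known from the documents and depends partly on which reading of the sentence applies. At 750 subjects the absolute error is under half a percentage point, and it grows as the number with diary data falls. It should be corrected because it is directional and easy to avoid, but no conclusion of the trial depends on it.

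**What to change.** In SAP 6.6.2.5, replace the sentence on the normal approximation with one to this effect: two-sided 95% confidence limits for every proportion in the solicited-event summaries will be computed by the exact (Clopper-Pearson) method. The Wilson score method would also serve. At 750 subjects it gives 0–0.51% for no events and 0.02–0.75% for one. No other section needs to change.

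The cost is one SAP sentence and one software option. Intervals become wider in sparse cells and stay practically the same for common events. At 20 of 750 the Wald upper limit is already 93% of the exact one.
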